3.2. Definition of Study Drugs

The study drug is open-label doxycycline 200 mg to be taken ideally within 24 hours but no later than 72 hours after condomless sexual contact. Participants will be instructed to take 200 mg of doxycycline at most once per 24-hour period regardless of the number of sexual acts occurring during this time period.

3.3. Sample Size Considerations

3.3.1. Sample Size Justifications

The sample size of 390 MSM/TGW in each cohort (MSM/TGW living with HIV and MSM/TGW on PrEP) has 80% power with 0.05 two-sided Type 1 error, for the endpoint of any lab-detected incident early syphilis, GC and/or CT infection, based on quarterly assessments for each person, 10% annual loss to follow-up and an intra-class correlation of 0.2. With these assumptions, a cohort of 390 of MSM/TGW living with HIV and 390 of MSM/TGW on PrEP (130 in the control and 260 in the intervention for each cohort) will provide 80% power to detect a decrease in quarterly STI prevalence from 10% to 5%, which corresponds to an annual reduction in combined STI incidence from 34% to 19%, assuming effective treatment.

We expect in the control arm approximately 5% of participants to have GC, 5% CT and 2% early syphilis at each quarterly visit; some will be diagnosed with more than one infection. We anticipate effectiveness of doxycycline PEP to be 35% for GC, 65% for CT and 65% for syphilis.

Sample sizes were computed using nQuery for repeated measures for two proportions, assuming four visits for each participant, and ratio estimators for the specified reduction. Approximately 10% annual loss to follow-up is assumed, because of partial information expected at some visits, this is approximated with sample size of 370.

Table 2 Power Table for N = 390; 2:1 randomization doxycycline PEP: SOC

Control arm quarterly prevalence	Intervention arm quarterly prevalence	Power to detect 50% reduction		Power to detect 65% reduction	
		ICC = 0.2	ICC = 0.1	ICC = 0.2	ICC = 0.1
10%	5%	80%	87%	96%	99%
7.5%	3.75%	68%	76%	90%	95%
5%	2.5%	51%	59%	77%	85%
3%	1.5%	35%	41%	57%	65%
2%	1%	26%	30%	43%	50%

3.3.2. Sample Size Re-estimation

At the point when enrollment is near completion, the study team will evaluate the expected power of the trial, based on the observed rate of infections, estimating intra-class correlation and retention to date in the trial. If the rate of the primary endpoint is substantially lower than anticipated, sample size re-estimation would be used to restore power to the extent possible, through additional enrollments, increase in person-time, or modification of risk criteria.

3.4. Randomization

The randomization is 2:1 for assignment to doxycycline PEP versus standard of care (no doxycycline PEP). Randomization is stratified by four sites, two primarily enrolling HIV-infected, and two HIV-uninfected participants, with block sizes selected with size randomly selected from between 15 to 30.

3.5. Clinical Assessments

Safety assessments are limited to the following:

- All grade 2 and higher hematologic and hepatic laboratory abnormalities that are attributed to doxycycline in the opinion of the site investigator
- All AEs meeting SAE definition
- All grade 3 and 4 adverse events judged to be associated with doxycycline (possibly, probably or definitely related)

In this open label trial, for those randomized to receive doxycycline PEP, all AEs and SAEs have attribution recorded as doxycycline-related or not doxycycline-related, in the judgment of the site investigator.

4. PLANNED ANALYSES

4.1. Interim Analyses

The trial will be monitored by an independent data monitoring committee approximately every 6 months. A single formal interim monitoring time is planned, when approximately half of the planned total enrollment have completed the 6-month visit, with stopping rules based on the achieved accrual of primary outcomes using the O'Brien-Fleming boundaries. Each cohort will be monitored separately. Stopping for both efficacy and lack of efficacy will be considered. However, a decision to stop for efficacy will need to balance the need for evidence assessing the potential harm of doxycycline-associated side effects.

4.2. Final Analyses

The final analysis will be conducted after database lock of all final (12 month) study visits.

5. GENERAL CONSIDERATIONS FOR DATA ANALYSES AND HANDLING

5.1. Data Presentation Conventions

Continuous variables (e.g., age) are summarized using descriptive statistics (the number of subjects with available data, the mean, standard deviation, median and minimum and maximum). Categorical variables (e.g., race) are summarized using counts and percentages. Percentages are calculated using the total subjects with data per treatment group.

5.2. Analysis Populations

5.2.1. ITT population

The intent-to-treat (ITT) population comprises all randomized participants. There are two ITT populations: HIV-uninfected MSM and TGW on PrEP; HIV-infected MSM and TGW.

5.2.2. Safety population

The 'Safety Population' is defined as all subjects who receive at least one dose of study medication. This population is expected to be identical to participants randomized to doxycycline PEP for this study.

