5 STUDY TREATMENT

5.1 Study product

Generic delayed release doxcycyline hyclate 200 mg capsules (Mayne Pharmaceuticals) will be provided by the study to participants randomized to open-label PEP, and to participants who choose to roll over to active doxycycline PEP following the 5/13/2022 closure of enrollment. Doxycycline DR is bioequivalent to

doxycycline hyclate IR. ^{60, 61} Doxycycline hyclate is widely available and FDA approved for the treatment of multiple infectious conditions. The full prescribing information can be accessed at: https://dailymed.nlm.nih.gov/dailymed/drugInfo.cfm?setid=cd2ab9b8-9619-4199-8a5d-83377b3274d1

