8. SAFETY AND TOLERABILITY

Statistical tests are not planned for adverse event comparisons between arms. Safety and tolerability will be assessed in the ITT cohort, or the doxycycline PEP arm only, given the open label nature of the cohorts.

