8.1. Adverse Events and Deaths

8.1.1. AE Definitions

Only the following AEs are recorded on eCRFs:

- All grade 2 and higher hematologic and hepatic laboratory abnormalities.
- All SAEs.
- In those randomized to doxycycline PEP arm, all grade 3 and 4 AEs with attribution to doxycycline in the opinion of the site investigator.

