8.1.2. Adverse Event Summary Tables

The number of Grade 2 and higher hematologic and hepatic AEs data will be tabulated by grade and arm. Subjects will be counted only once for each hematologic and hepatic report. For the doxycycline PEP arm, relatedness will be tabulated (see below of definition of relatedness).

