8.1.3. Listings of Serious Adverse Events (SAE), Adverse Event Dropouts, and Death

SAE data will be reported as related and not related. The two categories will be defined as follows:

- Related combines the options definitely, probably, and possibly
- Not related is not related.

Participant data listing for SAEs will be by cohort, and arm, sorted by reported date within participant. Unique information included on the first page of the listing contains SAE onset and resolution dates and times; verbatim description of SAE; severity and relationship to study medication, action taken, and outcome.

A tabulation will present participants who discontinue study drug prematurely for the doxycycline PEP arm due to an adverse event, and the reasons for discontinuations:

- Requirement for prohibited concomitant medications or other contraindication to doxycycline.
- Occurrence of an adverse event requiring discontinuation of doxycycline.
- Request by participant to terminate study treatment.
- Clinical reasons believed life threatening by the physician, even if not addressed in the toxicity section of the protocol.
- Requirement for chronic tetracycline use (>14 days).

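### The SAP's safety displays treat randomised arm as drug exposure, which no longer holds once control participants can roll over to study doxycycline

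*SAP*

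**What the plan says.** SAP section 5.2.2 gives a definition followed by a forecast. The definition rests on dosing: "The 'Safety Population' is defined as all subjects who receive at least one dose of study medication". The forecast equates that group with one randomised arm: "This population is expected to be identical to participants randomized to doxycycline PEP for this study".

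The safety displays then work by arm:

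- SAP section 8: "Safety and tolerability will be assessed in the ITT cohort, or the doxycycline PEP arm only".
- SAP 8.1.1, on which grade 3 and 4 events are recorded: "In those randomized to doxycycline PEP arm, all grade 3 and 4 AEs with attribution to doxycycline".
- SAP 8.1.2: "The number of Grade 2 and higher hematologic and hepatic AEs data will be tabulated by grade and arm". It continues: "For the doxycycline PEP arm, relatedness will be tabulated".
- SAP 8.1.3: "Participant data listing for SAEs will be by cohort, and arm, sorted by reported date within participant".
- SAP 8.2 summarises laboratory values for the doxycycline PEP arm only.

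The SAP is version 1.0 of 23 February 2021. It is based on Protocol Version 5.0 and records no revisions (section 10). Protocol Ver 9.0 of 27 May 2022 offers doxycycline to the standard-of-care arm (1.2.8). Section 5.1 supplies the study product to those randomised to PEP and "to participants who choose to roll over to active doxycycline PEP following the 5/13/2022 closure of enrollment". Section 6.3.24 puts the rollover and its start date on a CRF. The list of post-closure analyses in Protocol 10.5 covers STI incidence, resistance, adherence and acceptability. It contains no safety item.

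**The concern.** When the SAP was written, arm and exposure were the same thing for safety purposes. After rollover they are not: some people in the control arm are taking the drug whose safety is being described. If displays still follow the randomised arm, an event on doxycycline in a rollover control either counts against the comparator or has no place in any table.

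This matters because Protocol 1.2.8 justifies continued follow-up partly by the need for more tolerability data on doxycycline, and no analysis in either document collects the safety experience of those newly exposed. SAP section 8 plans no tests of adverse events between arms, so the descriptive displays are the whole of the planned comparative safety evidence.

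**Working it through.** The plan states no figure on this point, so there is none to reproduce. The check traces the definitions and then shows what can and cannot be sized.

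**1. Who is in the Safety population.** A control who takes study doxycycline meets the dosing definition in SAP 5.2.2 but was not randomised to doxycycline. The two sentences of 5.2.2 now describe different groups.

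**2. Where an on-drug event in a rollover control goes.**

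| Display | Rule as written | Result on the natural reading |
|---|---|---|
| Grade 2+ hematologic/hepatic AEs (SAP 8.1.2) | By arm | Counted under control |
| SAE listing (SAP 8.1.3) | By cohort and arm | Listed under control |
| Symptom comparator (Protocol 6.3.4) | Control arm asked the same questions | Counted under control |
| Related grade 3/4 AEs (SAP 8.1.1) | Those randomised to doxycycline | Left out |
| Relatedness (SAP 8.1.2; attribution in Protocol 7.2) | Doxycycline arm; those randomised to it | Left out |
| Laboratory summaries (SAP 8.2) | Doxycycline arm | Left out |

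**3. How many people could be affected.** Protocol 1.2.8 gives 554 participants at the interim review, and allocation is 2:1. That is about 554 × 2/3 = 369 on doxycycline and 554 × 1/3 = 185 in control. Uptake is not stated. If a share u of all controls rolled over, the dosed group would exceed the randomised doxycycline arm by u/2:

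- u = 25%: about 46 people, 12.5% larger
- u = 50%: about 92 people, 25% larger
- u = 100%: about 185 people, 50% larger. This is a ceiling, because controls who had already finished 12 months could not roll over and others could decline.

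**4. Direction and form of the dilution.** Let f be the share of control follow-up spent on doxycycline, r0 the risk off drug and r1 the risk on drug. If events are ascertained equally over time:

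observed control risk = (1 − f) × r0 + f × r1

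observed difference = (1 − f) × (r1 − r0)

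Protocol 1.2.1 quotes gastrointestinal side effects of 25% on PEP and 14% without it in the earlier doxycycline PEP trial. With those as r1 and r0, and f assumed:

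| f | Observed control risk | Difference (true 11.0 points) | Risk ratio (true 1.79) |
|---|---|---|---|
| 0.1 | 0.9 × 14 + 0.1 × 25 = 15.1% | 9.9 | 1.66 |
| 0.3 | 0.7 × 14 + 0.3 × 25 = 17.3% | 7.7 | 1.45 |
| 0.5 | 0.5 × 14 + 0.5 × 25 = 19.5% | 5.5 | 1.28 |

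**5. Why this is only an illustration.** The documents do not give f. The formula also fails for laboratory events, because ascertainment is unequal: those on doxycycline are tested at months 3 and 9, while the control CBC is scheduled at month 12 (Protocol 6.3.21). A control who rolled over and stayed on drug therefore has almost no scheduled safety laboratory value from before doxycycline, whatever f is. The exception is an earlier CBC used when the month 12 one could not be obtained.

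**The case against.** The best defence has five parts.

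- **Version lag.** The forecast in SAP 5.2.2 was correct under Protocol 5.0, and SAP section 1 foresees updates for amendments before database lock. This explains the gap but does not close it, since no update is supplied.
- **The definition is already exposure-based.** This is right, and the dosing sentence should stay. What fails is the forecast and the by-arm displays, and section 8 directs the assessment to the ITT cohort or the doxycycline arm.
- **No sentence assigns rollover events to control.** This also stands. Protocol 1.2.8 speaks of moving into the active arm, and Protocol 10.5 groups rollovers with doxycycline recipients for STI incidence and resistance. But 10.5 says nothing on safety, and the SAP's ITT and randomised-to wording points the other way. An ambiguity on this point needs a written rule.
- **The affected area is limited.** No between-arm AE tests are planned, only follow-up after rollover is touched, and the SAE listing carries onset dates that can be set against the CRF start date. Protocol 1.2.8 reports no doxycycline-associated AE of grade 2 or higher at the interim review. All of this limits the likely practical effect. It does not tell the analyst which column to use.
- **Leaving rollovers out of doxycycline-arm tables does not distort them.** This is correct. Those tables keep their own numerator and denominator, so the loss is of information.

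**Conclusion.** The point holds. Under Protocol Ver 9.0 the forecast in SAP 5.2.2 is false. Followed as written, the safety displays would on the natural reading put on-drug events under control in three places and leave them out of the doxycycline-arm displays.

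Three stronger conclusions are tempting and are not supported:

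- A reader might infer that the plan expressly assigns rollover events to the control column. It does not; that is the natural reading of by-arm displays.
- A reader might infer that omission, like misplacement, makes doxycycline look safer. Only misplacement dilutes a between-arm difference. Omission costs the on-drug data that the extended follow-up was meant to supply.
- A reader might suppose 3 to 6 of 12 control months on drug and conclude that an excess is understated by 25% to 50%. No document gives uptake or time on drug, and the formula assumes equal ascertainment, which fails for laboratory events.

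What can be said on size is the direction: if doxycycline raises the rate of an event, misplacement moves the by-arm contrast towards no difference. The 9.9 to 5.5 points above rest on assumed f, equal ascertainment and risks borrowed from the earlier trial.

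**What to change.** Amend the SAP before the final safety tables are produced:

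1. Delete the forecast sentence in 5.2.2 and keep the dosing definition. State whether doxycycline obtained from another provider ahead of the initiation visit (allowed in Protocol 6.3.24) counts as a dose.
2. Flag every AE, SAE, laboratory value and symptom report by treatment at onset, using the CRF start date. Symptoms are recorded as present or absent at visits, so state how a report spanning the start date is classified.
3. Show three groups with person-time: randomised doxycycline, control before doxycycline, and control after doxycycline.
4. Extend the recording of attribution, relatedness and related grade 3/4 events to everyone dosed, in both SAP 8.1.1–8.1.2 and Protocol 7.2.
5. Base the randomised comparison on follow-up up to one calendar date in both arms, such as the 5/13/2022 closure, and report later on-drug data descriptively. Setting all randomised doxycycline time against control time that ends at a self-chosen rollover date would not be a randomised comparison.
6. Add a safety item to Protocol 10.5.

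The cost is SAP and protocol wording, one derived flag, an extra column, and attribution of events in rollover controls by the sites where it was not recorded. The comparison loses follow-up after the cut-off. Control laboratory data before rollover will be sparse because of the month 12 schedule, and the report should say so. The primary efficacy analysis is unaffected.

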5.2.3. Blackbook responders

The subset of the ITT population that participates (i.e. contributes data) in the Blackbook app.

5.2.4. GC positive population

Post-baseline GC positive participants assessed for TCN resistance. Participants with positive GC will be assessed for culture based TCN resistance and for molecular resistance.

5.2.5. CT positive population

Post-baseline CT positive participants assessed for TCN resistance. Participants with positive CT will be assessed for molecular-based TCN resistance.

5.2.6. Syphilis positive population

Post-baseline Syphilis positive participants assessed for TCN resistance. Participants with incident syphilis will be assessed for molecular-based TCN resistance.

5.2.7. Nasal or oropharyngeal *S. aureus* carrier Population

Participants with nasopharyngeal cultures with *S. Aureus* growth assessed for TCN resistance.

5.2.8. Neisseria positive population

Participants with nasopharyngeal *Neisseria* growth assessed for oropharyngeal TCN resistance.

5.2.9. Hair population

Participants who have hair assessed for presence of doxycycline.

5.2.10. Gut resistome Population

50 HIV positive MSM and 50 HIV negative MSM/TGW assigned to the doxycycline PEP arm assessed for tetracycline resistance using rectal swabs.

5.2.11. Subgroups

The following are subgroups of interest:

- MSM only
- Age (< 30 vs. > 30)
- City (San Francisco/Seattle)
- Use of HIV PrEP (Event driven/Daily)

5.3. Handling of Missing Data

5.3.1. Missing Efficacy Endpoints

Complete case analysis will be used for the primary efficacy analysis, unless substantial imbalance (> 8%) in missing primary endpoint by arm occurs. Appropriate missing data methods (e.g. imputation) or causal estimation of direct effects will be conducted to assess the potential influence of differential missingness by arm.

6. STUDY POPULATION

6.1. Participant Disposition

A consort diagram will describe for each cohort separately the number screened, randomized, retained by visit, and contributing to the primary analysis endpoints by arm. Reason for screen-out and non-inclusion in the primary outcome will be summarized.

6.2. Screen Failures

Reason for screen failures will be summarized by arm and by site.

6.3. Protocol Deviations

A listing or summary of major protocol Deviations will be provided.

6.4. Study Termination Status

Reason for early study termination or study withdrawal will be enumerated and detailed. Study disposition at the time of a report will list those remaining in study follow-up, completed study follow-up, and early withdrawal (including deaths).

6.5. Demographic and Baseline Characteristics

The following baseline demographics and risk characteristics will be presented separately by cohort, by arm, and by site for the ITT cohort:

- Age in years
- Race/ethnicity
- Education
- Gender identity
- Sexual preference
- Sexual risk
 - Number and HIV serostatus of partners
 - Frequency of oropharyngeal, penile, and rectal exposure with and without condoms
 - STI(s) in year before enrollment
- alcohol use
- meth use
- IDU
- recreational drug use
- Living situation
- Health insurance
- Currently taking PrEP (Daily vs. event driven)/ART

6.5.1. Baseline Laboratory Data

Baseline bacterial STI diagnoses (GC/CT, Syphilis) detected by lab-based study testing will be reported for each cohort separately, by arm and by study site. Infections will be tabulated by sites(s) of infections

7. EFFICACY

7.1. General Considerations

Tabulations will be by study arm within each cohort, for each quarter of study follow-up (or at visits where evaluated). These will be reported in only the closed report during the study. Parallel tabulations will be given by study site only if substantive differences are observed between sites (which are not expected).

Inferential statistical tests will be two-sided and will be performed at alpha levels of 0.05 and 0.10 to declare the significance of main effects and interaction effects, respectively.

Analyses will be conducted separately for HIV-infected and HIV-uninfected cohorts for the primary endpoint, and for the combined cohort. All secondary endpoints will be conducted in the combined cohort.

7.2. Statement of the Null and Alternate Hypotheses

For both HIV-uninfected MSM/TGW on PrEP and HIV-infected MSM/TGW separately:

- H_0 : Use of doxycycline PEP does not have a differential effect on incidence of GC, CT and syphilis infections compared to the standard of care.

$$RR_{\text{any STI}} (\text{Doxo Arm}/\text{SOC Arm}) = 1$$

- H_A : Use of doxycycline PEP does have differential effect the incidence of GC, CT and syphilis infections compared to the standard of care.

$$RR_{\text{any STI}} (\text{Doxo Arm}/\text{SOC Arm}) \neq 1$$

7.3. Subgroup Analyses

Subgroup analysis of the efficacy of the intervention will be conducted for

- Age subgroups (</> 30).
- Report of STI diagnosis in prior year.
- Baseline viral suppression (< 50 copies) for HIV-infected men.
- On PrEP at baseline (Daily/Event driven/No) for HIV-uninfected men.

7.4. Multiple Comparisons and Multiplicity

No adjustments are planned for multiple comparisons.

7.5. Analysis of the Primary Efficacy Endpoint

7.5.1. Primary Efficacy Analysis

The primary analysis of efficacy will be conducted in the ITT cohort.

Endpoint definitions:

Primary endpoint: **Any STI** in the first, second, third or fourth quarter of follow-up, detected in post-baseline testing up to and including STI testing at months 3, 6, 9 and 12. Any STI diagnosed within 28 days of the same STI present at a quarterly visit will not be defined as an incident infection (suggesting incomplete treatment or persistent NAAT positivity without active infection, rather than re-infection). Incident infections detected and treated at interim visits after 28 days will be defined as incident infections for the current quarter. To avoid potential assessment bias, these will be handled in the analysis as if they would have been detected at a scheduled visit (months 3, 6, 9, and 12). Therefore, an STI diagnosed at 40 days after the month 6 visit will be carried forward as a primary event at the next scheduled visit (month 9). If a participant has more than one positive STI (either of the same or different bacterial infections at a scheduled visit) it will be counted as one primary event for that quarter. If scheduled visits are missed, infections will be assigned to the next scheduled visit.

All endpoints will be reviewed by the endpoint adjudication committee, blinded to doxycycline PEP assignment, for final determination, using most current CDC STI guidelines.

The criteria for an incident syphilis case will include a four-fold increase in non-treponemal titers (e.g., the RPR) and/or a consistent clinical presentation (e.g., characteristic chancre in primary syphilis which would be confirmed by a darkfield or reactive RPR without the requirement for a four-fold increase in titer).

Descriptive analysis

- The number of participants with any bacterial STI, and with each type of STI, will be summarized at each scheduled visit by arm.
- The number of STIs reported by each participant will be summarized at each scheduled visit by arm.
- For CT and GC, the anatomical site of infections will be detailed.

Statistical analysis

Comparison of STI incidence by arm will be conducted by estimating the relative risks of any STI over the 3, 6, 9, and 12 month visits using a modified Poisson model fitted using GEE methods to account for repeated observations from each participant, assuming an independent covariance structure, with site and study arm as the only covariates[1]. The test for significance will be a two-sided alpha = 0.05. 95% confidence intervals will be computed using robust standard errors.

The same analysis will be repeated for the individual STIs, potentially also by anatomical site.

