10.5 Analyses after 5/13/2022 closure to enrollment

Analyses after 5/13/2022 closure to enrollment and doxycycline provision to control will include the following:

STI incidence:

- Comparison of STI incidence per quarter in control arm before and after doxycycline initiation
- Comparison of STI incidence per quarter in all participants receiving doxycycline (including those in control arm after rolled over to receive doxycycline) compared to incidence on control arm prior to doxycycline roll over

Antimicrobial resistance

- Evaluation of tetracycline resistance in *Staphylococcus aureus*, commensal *Neisseria* in comparison to the control arm and to individual baseline
- Evaluation of genotypic or phenotypic tetracycline resistance in bacterial STIs in all participants who receive doxycycline compared to control arm participants, prior to receipt of doxycycline.
- Evaluation of changes in the gut microbiome and total gut burden of tetracycline resistance before and after taking doxycycline PEP

Adherence

- Evaluation of doxycycline coverage of qualifying sex before and after study closure 5/13/2022

Acceptability

- Proportion of control arm participants who opt to take study provided doxycycline. Control arm participants who terminate study participation will have the reason for termination recorded to determine if stopping to receive doxycycline outside of the study.

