7.5.5. Analysis of Tetracycline resistance

7.5.5.1. Primary analysis of TCN resistance in GC cases

The primary analysis of TCN resistance in GC will be conducted in the GC positive.

Descriptive statistics: Tabulations of resistance amongst cases (GC: TCN resistance testing missing, not resistant, resistant) will be reported at baseline, month 3, 6, 9, and 12 (and potentially interim visits) in each arm, for any infection site, and broken out by infection site. Additional descriptive information may also be included (i.e. change in MIC in GC cultures amongst those with repeat infections)

Statistical analysis: Assessment of odds of resistance amongst GC cases with resistance results will be assessed by arm using logistic regression with arm as exposure, adjusted for city. To account for repeated infections, repeated measures methods (GEE) will be used. Analysis comparing arms also potentially adjusted for age, race/ethnicity, baseline STI, baseline and follow-up sexual risk (number of partners, unprotected anal sex, employment). For the HIV-negative cohort, PrEP at baseline; for the HIV-positive cohort, viral suppression at baseline will also be considered.

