7.5.5.4. Analysis of TCN resistance in *S. aureus* carriers

The primary analysis of TCN resistance will be conducted in *S. aureus* cases detected at Baseline, 6- and 12-month visits.

Outcome: TCN resistance will be a dichotomous outcome defined as sensitive or resistance, based on e-Test cut-offs.

Descriptive statistics: Tabulations of TCN resistance in *S. aureus* cases (TCN resistance testing missing, not resistant, resistant) will be reported at baseline, 6- and 12-month visits in each arm. (site of *S. aureus*, if found, will not be known).

Statistical analysis: Assessment of difference in prevalence of TCN resistance by arm at each of 6 and 12 months will be assessed by estimating the relative risk of TCN resistance using modified Poisson regression. The model will assess the relative risk of resistance by arm, adjusted for study site at each time point. If an effect is found, assessment of a trend in time will be assessed by fitting a linear trend over study time. If prevalence of resistance is < 5%, analysis will pool across visits.

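### The SAP's by-arm STI and resistance models were not updated for the May 2022 roll-over, so control visits after doxycycline start count as standard of care

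*SAP*

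**What the plan says.** The SAP supplied is version 1.0 of 23 Feb 2021. It is based on Protocol v5.0 and records no revisions (SAP 10). Its rules on this point are:

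- Timing (SAP 4.2): "The final analysis will be conducted after database lock of all final (12 month) study visits".
- Population (SAP 5.2.1): "The intent-to-treat (ITT) population comprises all randomized participants".
- Primary STI model (SAP 7.5.1): "STI incidence by arm will be conducted by estimating the relative risks of any STI over the 3, 6, 9, and 12 month visits", by modified Poisson GEE with only site and arm as covariates.
- Gonorrhea resistance (SAP 7.5.5.1): "Assessment of odds of resistance amongst GC cases with resistance results will be assessed by arm using logistic regression with arm as exposure".
- S. aureus resistance (SAP 7.5.5.4): "Assessment of difference in prevalence of TCN resistance by arm at each of 6 and 12 months".

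None of these sets a data cut, ends control time at doxycycline start, or treats exposure as time-varying. The per-protocol rule in SAP 7.5.3 restricts the doxycycline arm only.

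Protocol v9.0 (1.2.8 and 6.3.24) lets control participants take study doxycycline until month 12 and records the start date on a CRF. Protocol 10.5 lists the analyses to be done after closure. The pooled STI comparison is "compared to incidence on control arm prior to doxycycline roll over", and resistance in bacterial STIs is "compared to control arm participants, prior to receipt of doxycycline". For S. aureus and commensal Neisseria the comparison is only "in comparison to the control arm and to individual baseline".

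**The concern.** Once control participants take doxycycline, randomized arm no longer separates doxycycline PEP from standard of care, which is the contrast in the hypotheses of SAP 7.2. If doxycycline has an effect, exposed control visits move the control arm toward the doxycycline arm and the estimate toward no difference.

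For STIs this dilutes a benefit. For resistance it understates a possible harm, which is the unsafe direction. Gonorrhea and S. aureus resistance form a primary objective (Protocol 3.1.2), and resistance is a stated reason for continuing follow-up after closure (Protocol 1.2.8). Month-12 swabs are the most exposed, because roll-over accumulates with time on study.

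The gap is wider than the three models above. The chlamydia and syphilis resistance models (SAP 7.5.5.2 and 7.5.5.3) are also by arm over all post-baseline visits.

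**Working it through.** **Reproducing the plan's power.** Inputs from Protocol 10.2 and SAP 3.3.1: 10% vs 5% quarterly risk, four visits, ICC 0.2, 246:123 evaluable per cohort, two-sided 0.05. Effective n = n × 4/(1 + 3 × 0.2): 123 gives 307.5 and 246 gives 615. A two-proportion test with pooled null variance then has 79.5% power (stated: 80%).

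**Dilution.** If a share f of control visits follows doxycycline start, control risk = 0.10 − 0.05f and RR = 0.05/(0.10 − 0.05f).

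**Assumptions for f** (the documents do not give it):

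- Time since enrollment at closure is uniform on (0, A) months. A = 22.4 is the span from 7/2020, when re-enrollment began (Protocol 6.8), to 5/13/2022; 18 and 27 give a range.
- Uptake u = 0.9, with 0.5 as a lower case.
- Lead case: doxycycline starts at about the next quarterly visit. An initiation visit inside the window includes the scheduled evaluations (Protocol 6.3.24), and the −10 week window covers 70 of every 90 days (Protocol 6.2.2).

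In the lead case, participants closed in their first, second or third quarter have 3, 2 or 1 exposed visits, so f = u × 3 × (3+2+1)/(4A) = 4.5u/A. In the window variant, those with more than 70 days left (20 of 90 days, 0.667 month of each quarter) start at once. On average 80/90 of that quarter is exposed, which adds 0.593u/A to f. As an upper bound, everyone starts at closure and f = 6u/A.

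| u = 0.9 | A = 18 | A = 22.4 | A = 27 |
|---|---|---|---|
| f, next visit | 0.225 | 0.181 | 0.150 |
| RR, next visit | 0.563 | 0.550 | 0.541 |
| RR, window variant | 0.573 | 0.557 | 0.546 |
| RR, upper bound | 0.588 | 0.569 | 0.556 |
| Month-12 control swabs exposed, next visit (9u/A) | 45% | 36% | 30% |
| Month 12, window variant (9.67u/A) | 48% | 39% | 32% |
| Month 12, upper bound (12u/A) | 60% | 48% | 40% |
| Month 6, next visit to window variant (3u/A to 3.67u/A) | 15–18% | 12–15% | 10–12% |

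At u = 0.5 the RR is 0.52 to 0.54, and 17 to 27% of month-12 control swabs are exposed.

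**Power at the planned size**, exposed visits kept as control versus dropped: f = 15%, 68.4% vs 77.6%; f = 20%, 64.0% vs 76.8%; f = 25%, 59.4% vs 76.0%. Dropping exposed visits costs less power than keeping them.

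**Precision of the fix at the enrolled size.** Assume the 554 enrolled at interim review (Protocol 1.2.8) split equally between cohorts and 2:1, giving 185:92 per cohort. With m visits kept per person, each arm contributes [(1−p)/p] × E[m(1 + 0.2(m−1))]/(n × E[m]²) to the variance of log RR.

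| | A = 18 | A = 22.4 | A = 27 |
|---|---|---|---|
| SE, full follow-up, no exposure | 0.283 | 0.283 | 0.283 |
| SE, control time ended at doxycycline start | 0.298 (+5%) | 0.294 (+4%) | 0.292 (+3%) |
| Control visits kept | 78% | 82% | 85% |
| SE, both arms cut at 5/13/2022 | 0.354 (+25%) | 0.336 (+19%) | 0.325 (+15%) |
| Visits kept in each arm (1 − 7.5/A) | 58% | 67% | 72% |
| Month-12 swabs kept in each arm (1 − 12/A) | 33% | 46% | 56% |

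Around RR 0.50, the 95% interval is about 0.28 to 0.90 when control time ends at doxycycline start. With the calendar cut it is 0.25 to 1.00 (A = 18) to 0.26 to 0.95 (A = 27).

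No resistance effect size is computed, because it would rest on an assumed true effect.

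**The case against.** **Protocol 10.5 was written for the roll-over.** It already limits pooled STI incidence and bacterial-STI resistance, including gonorrhea. That is so, but it does not say it replaces the SAP's by-arm models, and its S. aureus/Neisseria bullet has no limit on the control comparator. The individual-baseline half of that bullet is unaffected.

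**The SAP predates closure.** SAP 1 allows later versions and calls for a final one before database lock. This stands, so the point concerns the supplied text only. No SAP sentence says exposed visits count as standard of care; it follows from applying the models to all 12-month data.

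**Analysis by randomized arm is legitimate.** It is, but after roll-over it answers a different question from the hypotheses in SAP 7.2. It belongs as a sensitivity analysis.

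**Efficacy was settled at the interim analysis.** Agreed: that result is unaffected. Only the final reported relative risk would be diluted.

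**The figures rest on assumptions.** They do. If many re-enrolled participants finished before May 2022, the exposed share is lower. The gonorrhea resistance model uses cases, not visits: with the planned 35% gonorrhea effectiveness, 15 to 22.5% of control visits becomes about 10 to 16% of control gonorrhea cases. Recently exposed S. aureus swabs dilute fully only if resistance appears promptly.

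**The calendar cut buys no power.** Correct. Its z (0.693/SE) is 1.96, 2.06 and 2.13, the same as the diluted analysis; ending control time at doxycycline start gives 2.33 to 2.37. The cut's merit is that it removes the bias while treating both arms alike.

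**Conclusion.** The concern holds and should be fixed. The supplied SAP, followed as written, counts doxycycline-exposed control visits as standard of care in the STI, gonorrhea-resistance and S. aureus-resistance models, and one Protocol 10.5 comparator lacks the limit that two others carry. The direction, toward no difference, requires only that doxycycline has an effect and that some controls took it.

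The size depends on assumed uniform accrual, uptake and start time. In the lead case the STI dilution is modest (0.50 reads as 0.55 at the 22.4-month anchor). The month-12 resistance comparison is more exposed, with 36 to 39% of control swabs affected at that anchor. Confidence is high in the mismatch and low in any single figure for its size.

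**What to change.** 1. In the S. aureus/commensal Neisseria bullet of Protocol 10.5, limit the control comparator as the bacterial-STI resistance bullet does ("compared to control arm participants, prior to receipt of doxycycline").
2. Amend the SAP before database lock so that by-arm STI, gonorrhea and S. aureus analyses exclude control visits or samples after the recorded doxycycline start. Apply the same limit to the chlamydia and syphilis resistance models and to any by-arm Neisseria analysis.
3. For the primary STI effect, preferably cut both arms at 5/13/2022, which keeps the randomized comparison. For resistance, end control time at doxycycline start, which keeps later doxycycline-arm swabs, and use the calendar cut as a check.
4. Report the all-follow-up by-arm analysis as a sensitivity analysis, and state how the SAP models and Protocol 10.5 relate.

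The cost is one protocol clause and one SAP amendment; the start date is already on a CRF. SAP 7.5.5 has no commensal Neisseria model, so one would have to be written. Ending control time at doxycycline start raises the standard error by about 3 to 5%, keeps 52 to 70% of month-12 control swabs at 90% uptake, and carries some risk of informative censoring, which the calendar cut can check. The calendar cut raises the standard error by about 15 to 25%.
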